10.6 POWER AND SAMPLE SIZE

Power for this study was determined based on the following operating characteristics: (a) two sided type I error fixed at 0.0492, assuming one interim analysis, (b) 85% power, (c) minimum follow-up of 18 months, (d) 18-months event rate in the ICD alone group of 19% (e) expected 18-month relative rate reduction in the ICD + RSDN group of $\geq 40\%$, accrual period of 48 months and non-uniform accrual.

Under the above assumptions it is estimated that 70 events (or 462 patients) will be required to detect a relative decrease in the relative event rate reduction requiring any ICD therapy $\geq 40\%$ in the ICD + RSDN compared to the ICD alone group (19% vs. 11.4%) (Lachin, 1981).

Lost to Follow Up: The term "lost to follow-up" is used to define an individual who has withdrawn consent to be in the study or who can no longer be located or assessed. Such individuals represent those for whom primary outcome assessment is no longer possible. Since the primary outcome will be assessed by interrogating the ICD and since patients come back to

the hospital for regular check we do not anticipate a high rate of lost to follow-up. The estimated sample size accounts for 5% attrition due to withdrawal of consent.

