9.2 POST-PROCEDURE

9.2.1 POST-PROCEDURE FOLLOW UP

- All patients will be monitored to verify vascular hemostasis prior to discharge from the hospital.
- All patients will receive either oral aspirin (81-325 mg QD) or clopidogrel (75 mg QD) or warfarin or one of the NOACs (dabigatran, rivaroxaban, Apixaban) for at least 1 week upon discharge.
- Medication and adverse event review will be performed prior to discharge.
- Complications including vascular, stroke, heart failure etc., and presence of ventricular arrhythmias will be documented.
- ICD programming: (see below section 9.2.3)
- The total number of episodes of VT, ATP, and Shocks will be documented at all visits.
- The follow-up includes:
 - 1 Month (\pm 14 days):
 - History and Physical
 - ICD interrogation
 - Office BP measurements (x2) including orthostatics
 - Review of Medications and Adverse events
 - 6 Months (\pm 30 days):
 - History and Physical
 - ICD interrogation
 - Office BP measurements (x2) including orthostatics
 - Lab tests (CBC, Electrolytes, BUN/Cr)
 - BNP Level

- Review of Medications and Adverse Events
 - Repeat Renal Ultrasound or MR/CT Angiography
- 12 Months (\pm 30 days):
 - History and Physical
 - ICD interrogation
 - EKG
 - Office BP measurements (x2) including orthostatics
 - Lab tests (CBC, Electrolytes, BUN/Cr)
 - Blood for Renal Hormones (OPTIONAL)
 - BNP Level
 - Review of Medications and Adverse Events
 - Repeat TTE
- 18 Months (\pm 30 days):
 - History and Physical
 - ICD interrogation
 - Office BP measurements (x2) including orthostatics
 - Review of Medications and Adverse Events
- 24 Months (\pm 30 days):
 - History and Physical
 - ICD interrogation
 - Office BP measurements (x2) including orthostatics
 - Lab tests (CBC, Electrolytes, BUN/Cr)
 - BNP Level
 - Review of Medications and Adverse Events
- 36 Months (\pm 30 days):
 - History and Physical
 - ICD interrogation
 - Office BP measurements (x2) including orthostatics
 - Lab tests (CBC, Electrolytes, BUN/Cr)
 - BNP Level
 - Review of Medications and Adverse Events

Patients will be followed for a maximum of 36 months until the final patient reaches the 18 month follow-up time point. Once the final patient reaches the 18 month follow-up time point, all follow-ups will cease.

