10.7 INTERIM MONITORING GUIDELINES

The objectives of interim monitoring are to (1) monitor for safety, (2) track participant accrual rates, and (3) monitor the primary and secondary outcomes for early evidence of efficacy, harm or futility. To accomplish this, summaries of data quality, accrual, adherence, distribution of baseline factors, toxicity, study endpoints and other analyses as requested will be prepared for review by the Data Safety Monitoring Committee (DSMB).

The primary outcome of the trial, rate of first event requiring any ICD therapy, is the basis for formal interim analysis plan that follows. One interim analysis and one final analysis are planned for this trial, for a total of 2 analyses. These analyses will be performed when 0.5 and 1.0 fraction of the total number of events will have been observed. Since this study will have a target number of events of 70, we will have approximately 35 events observed between each analysis time.

We will use an alpha-spending O'Brien-Fleming sequential procedure as a guideline for decision making. At the interim analysis the value of the test statistic will be compared with the alpha spending function critical values. The two alpha values will be set at 0.0054 at the interim analysis and 0.0492 at the final analysis, which equate to critical values of 2.782 and 1.967 respectively. This monitoring plan maintains the overall type I error at 0.05, given one interim analysis.

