10.8 STATISTICAL ANALYSIS

The primary analysis will be an intent-to-treat analysis that will include all randomized participants regardless of treatment actually received or follow-up schedule.

Point Estimation and Interval Estimation: We will report maximum likelihood estimates for point estimation. For routine reporting, two-sided 95% confidence intervals for all parameters will be prepared.

Disposition of Participants and Baseline Comparisons: Summaries of all participants randomized and the number who complete visits at 30-days, and every 6 months after the day of randomization will be provided for each treatment group. The treatment groups will be compared at baseline with respect to demographics, baseline measurements related to efficacy and baseline measurements related to safety.

Univariate Analysis: All outcome measures will be described in a univariate analysis. For continuous variables means and standard deviations will be calculated. For discrete and dichotomous variables we will use contingency tables.

Analysis of Primary Endpoint: The primary endpoint of this study is defined time to first event requiring any ICD therapy (appropriate or inappropriate) or Incessant VT (VT occurring below the ICD rate cut-off); this will be assessed in the on-treatment patient cohort. An event requiring ICD therapy is defined as an anti-tachycardia pacing (ATP) or shock therapy. Time to event will be estimated using Kaplan-Meier curves. Survival time will be defined as the time (in months) between randomization and the occurrence of first ICD therapy. To compare the ICD+ RSDN arm with the ICD alone arm we will use a stratified log-rank statistic (using the stratification variables from the randomization procedure). A Cox proportional hazards model with treatment and other important prognostic factors as covariates will be used for the multivariate analysis of the times to first ICD therapy. Risk ratios and their 95% confidence intervals will be computed. Patients will be included in the analysis as censored if they are alive and free of ICD events at the end of the 18-month follow-up period. Although we do not anticipate interactions between treatment and stratification factors, formal tests for interactions will be assessed using proportional hazards models. A formal test of proportional hazards will assess the significance of

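### The 70-event target gives about 64% power, not the stated 85%: about 118 events are needed, and the plan conflicts on whether follow-up after month 18 counts

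*Combined protocol and SAP*

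**What the plan says.** Section 10.6 lists the design inputs: "two sided type I error fixed at 0.0492, assuming one interim analysis", 85% power, 18-month event rates of 19% (ICD alone) and 11.4% (ICD + RSDN), "minimum follow-up of 18 months", 48 months of accrual described only as non-uniform, and 5% attrition already allowed for. From these it concludes that "it is estimated that 70 events (or 462 patients) will be required to detect a relative decrease".

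Section 10.7 makes the event count operational: "Since this study will have a target number of events of 70, we will have approximately 35 events observed between each analysis time". The interim and final analyses fall at information fractions 0.5 and 1.0 of that total, with critical values 2.782 and 1.967.

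On follow-up, section 9.2.1 says: "Patients will be followed for a maximum of 36 months until the final patient reaches the 18 month follow-up time point". Section 10.8 specifies a stratified log-rank test and counts patients as "censored if they are alive and free of ICD events at the end of the 18-month follow-up period". The Design entry of the Protocol Summary gives a third figure, 12 months.

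**The concern.** The power of a log-rank test is set by the number of events. A target of 70 looks low for a hazard ratio near 0.57 at 85% power, and it is close to the count that 462 patients would produce in exactly 18 months. That suggests an expected count was entered as a required one.

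Because section 10.7 schedules both efficacy analyses on 70, the figure matters in practice. If the final test is run at 70 events, the chance of missing the design effect is about 36%, not 15%. The three statements on follow-up also leave an analyst unable to tell which events belong in the primary analysis, and that decides whether 462 patients can supply enough of them.

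**Working it through.** **Hazard ratio.** With exponential survival, the monthly hazards are −ln(0.81)/18 = 0.01171 (control) and −ln(0.886)/18 = 0.00672 (RSDN). HR = ln(0.886)/ln(0.81) = 0.5744 and ln HR = −0.5544.

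**Attempt to reproduce 70.** For two-sided 0.0492, z = 1.9669. For 85% power, z = 1.0364. The sum is 3.0033.

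- Schoenfeld: 4 × 3.0033² / 0.5544² = 117.4, so 118 events.
- Freedman: 3.0033² × (1.5744/0.4256)² = 123.4, so 124 events.
- Reading the 40% reduction as HR 0.60 makes it worse: 139 events (Schoenfeld).
- Other variants (one-sided tests, alpha 0.05, 80% or 90% power) also fail. The lowest is 81 events (one-sided, 80% power).

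The figure does reproduce as an expected count: 231 × (0.19 + 0.114) = 70.2.

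**Power at 70 events.** Schoenfeld: Φ(√70/2 × 0.5544 − 1.9669) = 63.8%. Freedman: 61.6%. Allowing for the two looks: 64.1%. Seventy events reach 85% only at HR = exp(−2 × 3.0033/√70) = 0.49.

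**Reading (b): event-free patients censored at 18 months.**

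- No loss: 462 × 0.152 = 70.2 events, power 63.9%.
- Exponential loss of 5% by month 18: 68.5 events, power 62.8%, so 70 events are not expected at all.
- Simulated log-rank power: 0.61 to 0.64.
- Patients needed for 118 events: 118/0.152 = 776 with no loss, or 118/(68.5/462) = 796 with loss.

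**Reading (a): follow-up counted to 36 months, closing at month 48 + 18 = 66.** For a patient entering at month u, follow-up is f = min(36, 66 − u). The event probability is λ/(λ+η) × (1 − exp(−(λ+η)f)), averaged over the accrual pattern, with η = 0 or −ln(0.95)/18 = 0.00285. The accrual patterns are assumptions, since the plan gives none.

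| Accrual | Events, no loss / 5% loss | Power, no loss / 5% loss | 70th event, 5% loss |
|---|---|---|---|
| Uniform | 118.4 / 113.2 | 85.3% / 83.7% | month 43.9 |
| Moderate ramp | 114.3 / 109.5 | 84.1% / 82.5% | month 48.2 |
| Linear ramp from zero | 110.3 / 105.8 | 82.8% / 81.2% | month 51.7 |

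Simulated log-rank power is 0.81 to 0.84. Stopping at the 70th event under this reading gives 0.62 to 0.64.

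**Interim timing under (a).** Thirty-five events are 35/118.4 = 0.30 to 35/105.8 = 0.33 of the information, not 0.5. With the printed bounds, two-look type I error moves from 0.0513 (fraction 0.5) to 0.0525 (fraction 0.31), a minor effect.

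**The case against.** The strongest reply is that the sample size may be right and only the event count mislabelled. Under uniform accrual with follow-up to 36 months, 462 patients yield 118.4 events and 85.3% power with no loss, and the period named in section 10.8 could loosely mean study closure when the last patient reaches 18 months. This has weight: power near 64% follows only if the 70-event trigger or 18-month censoring is applied. But both are what sections 10.7 and 10.8 literally say.

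It is also fair that the required count, about 118, is the same on either reading. Follow-up decides only whether 462 patients can supply it.

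The replacement figures under (a) are softer than the core result:

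- **Accrual.** With 5% loss, linearly decreasing accrual gives 120.7 events (86%) and quadratically increasing accrual 100.1 (79%).
- **Hazard after month 18.** The plan gives no later rate. If the hazard halved then (an assumption), events fall to about 88 to 92 and power to 74 to 75% with 5% loss.
- **Roll-in patients.** Section 8.1 counts up to one per site toward the enrollment ceiling without randomizing them. If 462 is that ceiling and all 20 sites use the option, 442 are randomized, giving 101 to 108 events and 79 to 82% with loss. The Protocol Summary's 231/231 split argues against this reading.
- **Attrition.** Under (b), dividing N by 0.95 gives about 818 patients rather than 796.

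These points widen the range the sponsor should consider. None makes 70 events sufficient.

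**Conclusion.** The concern holds. From the plan's own inputs, 85% power needs about 118 events (124 by Freedman), and 70 events give 62 to 64%. This rests on proportional hazards and on exponential survival to convert the 18-month rates to a hazard ratio; it does not depend on accrual or attrition.

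The consequences are alternatives, not cumulative. If the final analysis is run at 70 events, or patients are censored at 18 months, the chance of missing the design effect is about 36 to 37%. If all follow-up to 36 months counts and the final analysis waits for the last patient's 18-month visit, power is about 81 to 85%. That range assumes accrual between uniform and linearly increasing, at most 5% loss by month 18, and a constant hazard to month 36. In that case 70 is not the event total and 35 is not its half. The core error must be fixed before the event target is used to time an analysis.

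**What to change.** First reconcile the 18-month censoring (10.8), follow-up to 36 months (9.2.1), the 70-event trigger (10.7) and the 12-month follow-up in the Protocol Summary. Then take one route.

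**(a) All follow-up to 36 months counts.**

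- In 10.8, censor event-free patients at last follow-up.
- In 10.7, replace the 70-event trigger with a final analysis when the last patient reaches 18 months. A fixed target of 118 is the alternative, but 462 patients may fall short of it.
- In 10.6, restate expected events (about 106 to 118) and power (about 81 to 85%), recomputed from the sponsor's own accrual pattern, attrition, number randomized and hazard after month 18, each named.
- Place the interim at half the expected total (about 53 to 59 events), and recompute the final boundary from the actual information fraction.

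Cost: wording and restated figures, with no added patients or visits. The final analysis comes at month 66 rather than at the 70th event (about month 44 to 52).

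**(b) Patients are censored at 18 months, or the final analysis stays at 70 events.** Restate power as about 63 to 64%. Do not write in a 118-event target, because 462 patients cannot reach it under 18-month censoring.

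Cost: a less favourable stated power. Restoring 85% under 18-month censoring would take about 776 to 796 patients (about 818 if attrition is handled by simple inflation).

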The following primary endpoint will be assessed: Time to first event requiring any ICD therapy (appropriate or inappropriate) or Incessant VT (VT occurring below the ICD rate cut-off); this will be assessed in the on-treatment patient cohort. An event requiring ICD therapy is defined as an anti-tachycardia pacing (ATP) or shock therapy. The null hypothesis of principal interest is that there will be no difference between the two treatment arms in the time to first event requiring any ICD therapy (appropriate or inappropriate) or Incessant VT in patients randomized to ICD implantation with a single renal sympathetic denervation procedure compared to patients randomized to ICD implantation alone.

5.2 SECONDARY ENDPOINTS:

The following secondary endpoints will be assessed:

1. Appropriate ICD therapy assessed in the full intention-to-treat patient cohort
2. Inappropriate ICD therapy
3. Number of Hospitalizations for Cardiovascular Causes.
4. Total VT burden (Number of episodes).
5. All-Cause Mortality.
6. The occurrence of ICD storm, defined as ≥ 3 appropriate shock therapies within 24 hours.
7. Differences in BUN/creatinine measurements.
8. Procedure related adverse events including, but not limited to hematomas, pseudoaneurysms and renal artery stenosis.
9. Development of orthostatic hypotension
10. 30-day Major Complication Rate defined as death, stroke, MI or any other serious adverse events related to the treatment or procedure within the first 30 days or through hospital discharge (whichever is longer)

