9.1 PRE- AND ABLATION PROCEDURE

9.1.1 PRE-PROCEDURE

The following tests and procedures will occur before the ablation (within 30 days prior to randomization unless stated below):

- Recording of patient medical history (including details of VT both clinical/ICD)
- Recording medication history (including all AAD ever used, duration of use)
- Obtain β -HCG in females of child bearing age the morning of the procedure as per usual clinical practice
- Baseline assessment of arrhythmia burden and type: Office/inpatient records, ICD interrogation report
- If performed for any reason, collect any pre-procedural imaging: MRI/CT and Renal Ultrasounds within 6 months of procedure
- Baseline laboratory, including complete blood count, standard electrolyte panel, renal function, and brain natriuretic peptide levels.
- Baseline Transthoracic Echocardiogram within 3 months of procedure
- Baseline Office blood pressure. Proper blood pressure measurement technique is essential: i) patient should sit quietly in a chair with his/her back supported for 5 minutes before taking the measurement; ii) use of the correct cuff size with the air bladder encircling at least 80% of the arm (the adult large cuff for the majority of patients); iii) support the arm at heart level during the cuff measurement; iv) a minimum of 2 readings should be taken at intervals of at least 1 minute and the average of those readings should be taken to represent the patient's blood pressure; v) the blood pressure should be measured
- Consent must be obtained either before, or within 24 hours of ICD placement. The patient may undergo ICD placement up to 1 month (30 days) before randomization. The patient must undergo ICD placement and Renal Angiography (Control Group) or ICD placement and RSDN (Study/Experimental Group) within 1 month (30 days). All ICDs must be devices from Boston Scientific (either single-, dual-, subcutaneous, or biventricular devices).
- Randomization into one of two groups will be performed by opening the Randomization envelope after Renal Angiography.

Study/Experimental Group: These subjects will undergo catheter-based sympathetic renal denervation.

[figure not shown]
Placebo Control Group: These subjects will receive no further intervention.

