9.3.2 CLINICAL EVENTS COMMITTEE

A separate Clinical Events Committee (CEC) composed of 2 independent cardiologists/ electrophysiologists will adjudicate all ICD events in this study.

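### Incessant VT below the ICD rate cut-off is part of the primary endpoint, but the plan gives it no working route into the analysis, so a patient with slow incessant VT and no ICD therapy would be counted as event-free

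*Combined protocol and SAP*

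**What the plan says.** **Endpoint.** Sections 5.1, 10.3 and 10.8 define the primary endpoint as time to first event requiring any ICD therapy (ATP or shock) or "Incessant VT (VT occurring below the ICD rate cut-off". Neither the term incessant nor the cut-off is defined further.

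**Assessment.** The only method named for the primary outcome is in the loss-to-follow-up paragraph of 10.6: "Since the primary outcome will be assessed by interrogating the ICD".

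**Device range.** Section 9.2.3 lists a monitor zone of 130-170 bpm, a VT zone of 175-195 bpm and a VF zone at 200 bpm. The monitor row of the detection table is blank.

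**Adjudication.** Under 9.3.2 the Clinical Events Committee "will adjudicate all ICD events in this study".

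**Analysis.** Section 10.8 measures survival time "between randomization and the occurrence of first ICD therapy". Patients are "censored if they are alive and free of ICD events at the end of the 18-month follow-up period". Section 10.7 describes the primary outcome for the interim analysis as the rate of first event requiring ICD therapy, without incessant VT.

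**Other data collected.** Section 9.2.1 says "The total number of episodes of VT, ATP, and Shocks will be documented at all visits" and, after the procedure, "presence of ventricular arrhythmias will be documented". Table 1 schedules history and physical, ICD interrogation and adverse-event review at every follow-up visit, and a follow-up EKG at 12 months only. Cardiovascular hospitalizations are a secondary endpoint (5.2).

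**The concern.** One component of the endpoint is defined by lying below a device threshold, while the device is the only named instrument. The committee's charge and the analysis rules then refer to device therapy or device events alone. The component is therefore in the definition but missing from the steps that would turn an occurrence into a counted event.

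A programmer following 10.8 literally has no event time to assign to incessant VT that triggers no therapy, and would censor that patient as event-free. The reported result would then be time to first ICD therapy, presented as the wider composite. At the least, events are lost. If the lost events were unevenly split between the arms, the treatment comparison would be biased as well.

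**Working it through.** **1. Following a patient through the plan**

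Take a patient with incessant VT and no ATP or shock up to month 18.

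- *Rate within 130-170 bpm.* If the cut-off means the VT therapy zone (175 bpm), this meets the endpoint definition and interrogation can show it. The committee may or may not regard a monitor-zone record as an ICD event. Under 10.8 there has been no ICD therapy, so no event time exists.
- *Rate below 130 bpm.* This meets the definition too. No programmed zone covers it, so it is probably not logged; the documents do not say what the device stores there. It could surface through a visit history, an EKG, an adverse-event report or a hospital admission. No text carries that record to the committee or to the endpoint, and 10.8 again supplies no event time.
- *If the cut-off means the lowest programmed zone,* the whole component lies below 130 bpm and the second case applies throughout.

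On each reading the literal outcome is censoring as event-free. At baseline, by contrast, 9.1.1 takes arrhythmia burden from "Office/inpatient records, ICD interrogation report". No equivalent pairing of sources is stated for the endpoint during follow-up.

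**2. The plan's event count**

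Inputs from 10.6: 231 patients per arm, 18-month rates of 19% and 11.4%, two-sided alpha 0.0492.

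- Expected 18-month events: 231 × 0.19 + 231 × 0.114 = 43.9 + 26.3 = 70.2, matching the stated 70.
- Hazard ratio under exponential times: ln(1 − 0.114) / ln(1 − 0.19) = 0.574.
- Schoenfeld power: Φ(√(E/4) × |ln HR| − 1.967). With E = 70.2 this is 64%. That 70 events fall short of the stated 85% is a separate matter; 64% serves here only as the baseline.

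**3. Equal under-capture in both arms**

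The documents give no frequency of slow VT, so the fraction q of events missed is an assumption. Both rates are multiplied by (1 − q).

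| q | 18-month events | HR | Power |
|---|---|---|---|
| 0% | 70.2 | 0.574 | 64% |
| 5% | 66.7 | 0.576 | 61% |
| 10% | 63.2 | 0.577 | 59% |
| 20% | 56.2 | 0.580 | 53% |

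The hazard ratio barely moves; the cost is events and power.

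**4. Under-capture in the RSDN arm only, with no true effect**

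The apparent HR is ln(1 − 0.19(1 − q)) / ln(1 − 0.19). The chance of a significant result is the two-sided rejection probability at 70 events.

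| q | Observed RSDN rate | Apparent HR | Chance of significance |
|---|---|---|---|
| 5% | 18.1% | 0.945 | 6% |
| 10% | 17.1% | 0.890 | 8% |
| 20% | 15.2% | 0.782 | 18% |

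This table shows sensitivity only. Nothing in the documents supports any particular q.

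**The case against.** A reader might infer that the device is blind below 130 bpm, that slow VT therefore goes unseen, and that VT merely slowed by RSDN would be scored as prevented. The documents do not support that reading.

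- No section says what the ICD stores below 130 bpm. The limit is inferred from the zone table.
- VT at 130-170 bpm lies below the therapy zone but inside the monitor zone, so interrogation can show it.
- The 10.6 sentence explains why little loss to follow-up is expected. It does not say that interrogation is the sole source.
- VT episodes, ventricular arrhythmias, adverse events and cardiovascular hospitalizations are all collected. Slow VT may well be found.
- Nothing says that RSDN slows VT. The rationale in section 3 argues for fewer arrhythmias through lower sympathetic tone.
- The one-arm table applies q to every primary event, including inappropriate therapies, which cannot be slowed VT. The 20% row needs about 8.8 of 43.9 RSDN-arm events to fall below the recordable range, and none of those patients to receive a later therapy.

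All of this stands, and it removes any claim of a demonstrated bias. It can also be said that 10.8 repeats the full endpoint definition before its shorter phrasing, so the intention is clear and the reference to first ICD therapy may be shorthand. That does not settle the matter: the event-time and censoring sentences are the operative rules, and 10.7 and 9.3.2 use the same narrower terms. The other data are collected but nowhere tied to the endpoint.

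**Conclusion.** The point holds as an inconsistency between the endpoint definition and the rules for ascertaining, adjudicating and analysing it. Followed literally, the plan leaves incessant VT without therapy uncounted, even where it has been documented. This rests on the text of 9.3.2, 10.7 and 10.8 and needs no assumption about the device. That VT below 130 bpm is probably not logged is a further inference and makes the gap wider.

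The size and direction of the effect on the result are unknown, because the documents give no frequency of slow VT in either arm. Under equal loss of 5% to 20%, about 3.5 to 14 of 70.2 events disappear (70.2 − 66.7 and 70.2 − 56.2) and the hazard ratio stays near 0.58. A bias towards RSDN arises only if slow VT is more frequent in that arm, which the documents do not address. The hazard ratios in the one-arm table are hypothetical and should not be cited as an expected bias.

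**What to change.** 1. **Sections 10.8 and 10.7.** Define event time as the first of ICD therapy or incessant VT, censor only patients free of both, and use the same event for the interim analysis. Without this, better detection changes nothing.
2. **Sections 5.1, 10.3 and 10.6.** State what the rate cut-off refers to and what qualifies as incessant. State that the component is ascertained from the ICD log, including the monitor zone, and from ECG, telemetry and hospital records gathered at scheduled visits in the same way in both arms.
3. **Section 9.3.2.** Extend the committee's charge to all candidate primary-endpoint events, preferably blind to allocation, because the operating physician knows it (9.1.3).

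If the sponsor does not want sources outside the device, the alternative is to restate the component as VT within the device's monitored range and align 10.7 and 10.8 with that. No change to ICD programming is proposed.

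The cost is protocol and SAP wording, one CRF item at visits already scheduled, and some further records for the existing committee. The downside is that VT found outside the device is detected less systematically and may depend on unblinded staff. Uniform collection in both arms and blinded adjudication reduce that risk but do not remove it.

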Design:	This study is a prospective, multicenter, single-blinded, randomized (1:1) control trial evaluating the effectiveness of RSDN in the primary prevention of ICD therapy in patients with ischemic or non-ischemic ventricular dysfunction who are to receive an ICD for either i) secondary prevention, or ii) primary prevention + inducible VT by programmed ventricular stimulation at the time of ICD implantation. These patients will be randomized to ICD alone or ICD + RSDN. Subjects will only be eligible for this study if they are \geq 18 years of age and have a history of structural heart disease (post-MI, dilated cardiomyopathy, sarcoid myopathy, hypertrophic cardiomyopathy, etc.), and are planned for ICD implantation for: i. Secondary prevention (e.g.: VT/VF arrest, sustained VT, syncope/inducible VT) ii. Primary prevention + inducible MMVT during induction via ICD lead testing. In addition, eligible patients will have accessible renal vasculature (as determined by renal angiography).
	The patient will be blinded to the results of randomization. Once randomized, study group subjects will undergo a strategy of catheter-based renal sympathetic denervation + ICD implantation (if not already present). Control patients will receive standard ICD implantation alone (if not already present). Follow-up will be conducted in regular intervals over a 12-month period.
Enrollment:	Total: 462 subjects (231 control group, 231 study group)
	An interim safety analysis will be performed after the first 50 subjects (25 control group, 25 study group) have completed their 6-month follow-up visit.
Clinical Sites:	
• Icahn School of Medicine at Mount Sinai• Homolka Hospital, Prague, Czech Republic• Heart Center U SV. Anny Hospital, Brno, Czech Republic• Massachusetts General Hospital• Regional Cardiology, Sacramento, California• Medical University of South Carolina• Florida Hospital, Orlando, Florida

	
 • Other Sites TBD
Time Course:	Enrollment: Over 4 years

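### The 70 events, 462 patients, 85% power and 5% attrition in section 10.6 do not fit together: 70 is the no-loss 18-month count and gives about 64% power

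*Combined protocol and SAP*

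**What the plan says.** The inputs are in section 10.6: "two sided type I error fixed at 0.0492, assuming one interim analysis", 85% power, at least 18 months of follow-up, a control event rate of 19% at 18 months, a 40% relative reduction (to 11.4%), and 48 months of accrual described only as non-uniform. The result is given as "Under the above assumptions it is estimated that 70 events (or 462 patients) will be required to detect" this difference. The same section closes by saying that "The estimated sample size accounts for 5% attrition due to withdrawal of consent". It shows no sample size before inflation, no inflation formula and no accrual shape.

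The event figure is then used operationally. Section 10.7 says "this study will have a target number of events of 70", and places the one interim analysis at half of it, about 35 events.

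Two other places decide how many events will be counted. Section 10.8 (Analysis of Primary Endpoint) treats patients as "censored if they are alive and free of ICD events at the end of the 18-month follow-up period", and its Missing Data paragraph censors patients who withdraw consent at the time of withdrawal. Section 9.2.1, however, follows patients for up to 36 months, until the last patient reaches 18 months. Allocation is 1:1; the Protocol Summary gives "Total: 462 subjects (231 control group, 231 study group").

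**The concern.** With equal arms, the average 18-month event probability is the mean of 19% and 11.4%, and multiplying it by 462 returns 70. That product has no loss in it, although the section says loss is allowed for and section 10.8 removes withdrawn patients from risk. The event target and the attrition statement therefore cannot both describe the same 462 patients under an 18-month cut.

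It also suggests that 70 is the number of events expected from 462 patients rather than the number needed for 85% power, which is how section 10.6 presents it. The two must agree for the stated power to hold. At stake is the timing of both formal analyses: a final analysis triggered at 70 events would have much less power than stated, and under strict 18-month censoring even 70 is more than the design would be expected to deliver.

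**Working it through.** **Inputs.** From section 10.6: alpha 0.0492 two-sided (critical value 1.967 in section 10.7), power 85% (z = 1.036), rates 19% and 11.4%, 70 events, 462 patients, 5% attrition, 48-month accrual. From section 10.8: censoring at 18 months and at withdrawal. From section 9.2.1: follow-up capped at 36 months. Assumptions of this check: exponential event times, and the timing of loss as stated in each step.

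**1. Reproducing 70.** Mean event probability = (0.19 + 0.114)/2 = 0.152. Then 462 x 0.152 = 70.2 (43.9 control + 26.3 RSDN), which rounds to 70. The match is to rounding only; any total from 458 to 463 also rounds to 70.

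**2. Events by 18 months with 5% loss.**
- Lost patients contribute nothing: 462 x 0.95 x 0.152 = 438.9 x 0.152 = 66.7.
- Loss at a constant rate over the 18 months: the monthly event rates are -ln(0.81)/18 = 0.01171 and -ln(0.886)/18 = 0.00672, and the loss rate is -ln(0.95)/18 = 0.00285. The event probability in each arm is rate/(rate + loss) x [1 - exp(-18 x (rate + loss))]. Control: 0.804 x (1 - 0.7695) = 0.1854. RSDN: 0.702 x (1 - 0.8417) = 0.1112. The mean is 0.1483, and 462 x 0.1483 = 68.5.

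**3. Could 462 already be inflated?** 440 x 1.05 = 462 and 220 x 1.05 = 231, both exact. So it could. The matching no-loss event count would then be 440 x 0.152 = 66.9, and 70 would have been computed from the inflated total.

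**4. Events needed for 85% power.** Hazard ratio = ln(0.886)/ln(0.81) = 0.574, with log -0.554. Schoenfeld: 4 x (1.967 + 1.036)^2 / 0.554^2 = 117.4, so 118 events. Freedman's formula gives 124. Taking the 40% reduction as a hazard ratio of 0.6 gives 139 (Schoenfeld) or 145 (Freedman). No variant tried gives 70; the lowest, one-sided with 80% power, gives 81.

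**5. Power at the available events.** Power = Phi(sqrt(events) x 0.554/2 - 1.967).

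| Events | Source | Power |
|---|---|---|
| 70 | stated target | 63.8% |
| 68.5 | 18-month cut, loss spread | 62.8% |
| 66.7 | 18-month cut, loss at entry | 61.7% |
| 118 | required | 85% |

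From 70 to 66.7 events, power falls by 63.8 - 61.7 = 2.1 points.

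**6. If events after 18 months count.** This takes 48-month accrual, follow-up to the earlier of 36 months or the last patient's 18-month visit, and the constant loss rate of step 2. The accrual shapes are assumptions, since the plan gives none.

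| Accrual | Events from 462 after loss | Power |
|---|---|---|
| Linearly increasing | about 106 | about 81% |
| Uniform | about 113 | about 84% |
| Linearly declining | about 121 | about 86% |

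All are far above 70.

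**The case against.** The strongest reply is that the plan attaches the 5% to the sample size, not to the event count. Since 462 is exactly 440 x 1.05, the allowance may be inside 462, with 70 obtained afterwards from the inflated total. This stands. A reader might infer from step 1 that 462 contains no attrition allowance at all; the documents do not support that, because they show neither the total before inflation nor the formula. What the reply does not do is reconcile the figures: if 462 is inflated, the 70-event target was set as though nobody would be lost.

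A second reply is that 462 may come from a survival calculation that uses follow-up beyond 18 months. This also stands in part. A reader might infer from uniform accrual (118 events without loss, 118 needed) that the longer follow-up leaves no room for attrition either. That does not hold: the plan says accrual is non-uniform, and with linearly declining accrual about 121 events remain after 5% loss, which is enough. With increasing accrual it is not. The documents cannot decide between these. On either shape, though, 70 is not the event count that belongs with 462 patients, so this reading rescues the patient number and not the event target.

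A third reply is that attrition matters little here. That is correct: it costs about 2 points of power. The weight of the point lies in the mismatch between 70 events and 85% power.

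**Conclusion.** The point holds as an inconsistency among the stated figures, not as a finding about how 462 was derived.

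- Under the 18-month censoring of section 10.8 and 5% loss, 462 patients are expected to give 66.7 to 68.5 events at the planned effect, below the target of 70.
- Seventy events give about 64% power for 19% versus 11.4% at two-sided alpha 0.0492. The stated 85% needs about 118. This is the larger error and does not depend on attrition.
- If later events count, the expected number is roughly 106 to 121 after loss, and stopping at 70 would end the trial well before the information that 85% power requires.

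The first result rests on the 18-month cut and on the assumed timing of loss. The second rests on proportional hazards with exponential event times, used to turn the two 18-month rates into a hazard ratio of 0.574. The third rests on assumed accrual shapes. The documents leave open both the origin of 462 and the follow-up period to be analysed.

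**What to change.** In section 10.6:

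1. Reconcile the 18-month censoring in section 10.8 with the follow-up to 36 months in section 9.2.1, and say whether primary events after 18 months count.
2. State the sample size before inflation, the inflation formula and the accrual shape.
3. Give the expected events after 5% loss under the follow-up actually analysed, with the power at that number (about 62 to 63% under the 18-month cut).

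Then reset the event target in section 10.7, and the half-information interim count, to match. If the target became 118, for example, the interim would fall at 59 events rather than 35.

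This is a change of text and needs no extra patients. The price is either a less favourable stated power, if the 18-month cut is kept, or a later event-driven analysis, if longer follow-up is counted. The plan should not simply declare that 462 contains no attrition allowance unless the sponsor's original calculation shows it.
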